5.0 Study Design

This is an open-label, interventional trial to evaluate reward system modulation (detected by neuroimaging) in response to opioid antagonism (i.e., naltrexone) in adolescents aged 13-21 years with an eating disorder characterized by the target behaviors of binge eating and/or purging (e.g., AN-

SHORT TITLE: Naltrexone Neuroimaging

BP, BN, BED). A pre/post design completed on the same day will be employed to quantify *within-individual change* while reducing potential confounding due to known neuroimaging variables (e.g., menstrual phase, treatment changes) that may occur with time elapsed between study visits.

Up to 50 individuals may be enrolled to meet our objectives.

6.0 Inclusion and Exclusion Criteria

Inclusion Criteria

- Adolescents aged 13-21 years
- *Eating disorder diagnosis per DSM-V criteria that is characterized by binge eating (defined as loss of control of eating resulting in large amount of food consumed in a short period of time) and/or purging (e.g., vomiting, excessive exercising, laxative use)*
- *Stable medication regimen (no dose or drug changes in the past 4 weeks)*
- *Participant and parent/legal guardian (if under 18 years) are willing and able to provide informed permission/assent/consent for the study*

Exclusion Criteria

- *Pregnant (via UCG)*
- *Prior hypersensitivity reaction to naltrexone (e.g., anaphylaxis)*
- *Non-removable metal in the body*
- *Current naltrexone use*
- *Self-reported opioid use in the past 7 days*
- *A language barrier (e.g., non-English speaking) for the participant that precludes communication and/or ability to complete all study-related requirements.*

English speaking participants whose parent/guardian are non-English speaking may be consented using a translated PAC form. Participants will have suitable English proficiency to complete study questionnaires and logs. Determination of proficiency will be at the discretion of the PI. Non-English speaking participants are excluded because the validated questionnaires used in this study to measure eating disorder symptomatology (EPSI) is not yet available in languages other than English. This assessment was chosen because of the ability to discriminate eating disorder behaviors and validation in the target age range. It is also the main assessment used in the CM Eating Disorder Center and thus parallels clinical practice.

Non-English Speaking Subjects:

- Parent/guardians only
- language(s) other than English understood by prospective parent/guardians: Spanish
- ORI Translation Program to translate the PAC form

7.0 Prescreening

Prescreening will occur through discussion with treating clinicians and review of medical records (through automated EHR report for those with eating disorder diagnoses). We anticipate that ~5% of those pre-screening will enroll, thus we estimate pre-screening up to 1000 individuals.

8.0 Recruitment

Recruitment will occur throughout the region using various means of IRB approved media to achieve target enrollment, including the following:

SHORT TITLE: Naltrexone Neuroimaging

- Social media
 - Potential participants may learn about this study from information posted on the internal Children's Mercy Hospital website and on the Children's Mercy Research Institute (CMRI) public facing website. Social media platforms, such as Twitter and Facebook, may be used to disseminate study information. The social media platforms will reference or link to study information available on the CMRI website. Use of social media to share study information will be compliant with any existing CMH policies. The use of social media to share study information will not begin until these policies have been developed. Presentation of study information and content posted on the CMRI website will be at the discretion of the Digital Team, Research Administration, and the research team. Modification of images may be applied by the Digital Team and Research Administration to be consistent with the aesthetic of the CMRI webpage. All study information will be approved by the IRB.
- Flyers
- Email blasts (e.g., Daily E-news)
- Direct communication from study staff to potential participants (identified by pre-screening) via available contact information.
 - Self-referral: Individuals who express interest may contact study staff or click the link provided on recruitment materials. If the potential participant would like to receive more information regarding the study, they can also complete a contact form so a team member may contact the individual.
 - Provider referral: Potential participants may be referred to the study team by their health care provider. The provider may share the potential participant's contact information if they obtain permission to do so.

A member of the research team may call or email potential participant up to three times using CHM email, Microsoft Teams or CMH phones. When contacted, individuals will undergo a brief screen to determine potential eligibility. Interested individuals will then schedule a time (virtually or in person) to fully explain the study, answer questions and obtain informed consent. This may occur at initial contact based on participant preference.

9.0 Study Procedures

The study will involve a screening encounter and one study day.

Study Visit Element	Main Procedures/Data Collected	Approximate Clock Time
Screening and Consent	Inclusion/exclusion criteria, Consent	In person, telephone or e-consent prior to study visit
I/E confirmation and medical History	Inclusion/exclusion criteria review and confirmation, medical history, anthropometrics, pregnancy test (if applicable)	7 am
Meal #1 (1 hour before scan #1)	Standardized CHO:PRO:FAT content	8 am
Baseline/pre-dose measures	Impulsiveness (BIS-brief), negative urgency (UPPS-P subscale); delayed discounting, blood draw (targeted metabolomic panel, genetic analysis)	8:20 am
fMRI scan #1	Hunger rating, reward related tasks (PFV, MID)	9 am
Naltrexone (NTX) dosing	Naltrexone 50 mg PO 2 hours prior to scan #2	10:30 am
Meal #2 (1 hour before scan #2)	Standardized CHO:PRO:FAT content	11:30 pm

SHORT TITLE: Naltrexone Neuroimaging

fMRI scan #2 (2 hours post-NTX)	Hunger rating, reward related tasks (PFV, MID)	12:30 pm
Pharmacokinetic analysis	3 mL blood samples - pre-dose, 0.5, 1, 1.5, 2, 3, 4, 6, 7 hours post-naltrexone dose.	5:30 pm (last PK draw & study end)

Screening and consent. The study will be reviewed in depth with the participant and his/her parents/legal guardian when applicable. They will be provided sufficient time to review the PAC form, have all questions answered, and concerns addressed. If they agree to participate, they will sign the PAC form. This may occur in person, over the phone (using telephone script) or via e-consent. In the event the parent/guardian is non-English speaking, interpreter will be offered along with provision of translated PAC form. The participant must have English proficiency to complete study procedures (see inclusion criteria).

Screening failures (i.e., participants meeting any exclusion criteria) may be screened again at a future time point at the discretion of the Principal Investigator.

Pre-visit Planning. Scheduled participants may be contacted ahead of study with a reminder of their study appointment. Once PAC has been obtained, participants will be reminded to avoid food for 4 hours prior to study day.

Assessments (including categories of data collected). Self-report data will be captured via electronic surveys (e.g., Research Electronic Data Capture -REDCap), structured interview, study records. Anthropometrics. Height, blind weight will be obtained; body mass index (BMI), BMI z-score, % ideal body weight will be calculated. Structured interview. Study staff will obtain participant demographics, ED, medical, family & menstrual history. Confidential social history will be obtained via self-report electronic survey. Laboratory. Urine drug panel will objectively assess illicit substance use (e.g., nicotine, THC) at baseline along with urine pH and specific gravity and used as covariates in analysis. Eating Disorder Symptom Burden. The EPSI will evaluate symptom burden at baseline. The EPSI has excellent validity and reliability derived from a diverse population, has published normative data(8, 9) and includes various sub-scales (e.g., body dissatisfaction, cognitive restraint) that will allow characterization of our sample. Hunger. Before each scan, hunger will be assessed. Safety. Baseline heart rate and blood pressure will be recorded. Physical symptoms that may occur after naltrexone administration will be assessed.

Reward System Modulation by fMRI. Each participant will undergo two fMRI scans on the same day. Scan #1 (pre) will be in the fed state *before* naltrexone administration. Scan #2 (post) will be in the fed state 2 hours *after* naltrexone. Each scan will last approximately 1 hour and involve two reward activation paradigms(10-12): passive food view (PFV) and monetary incentive delay (MID). These two reward activation paradigms provide distinct insight and will generate pilot data to support the choice of the optimal paradigm for further testing of reward system modulation in adolescents with eating disorders. PFV provides a paradigm that is relevant to the target behaviors (i.e., binge eating, purging), has been evaluated in ED patients, in response to naltrexone in adults, and is expected to activate food cue-reactivity regions (e.g., prefrontal cortex). MID is a widely used paradigm in adolescents to detect reward anticipation and receipt particularly in the striatum and is currently being used to study the developmental trajectory of reward processing in the longitudinal Adolescent Brain Cognitive Development (ABCD) trial. To the greatest extent possible, we will harmonize our fMRI parameters with those published for ABCD.

Opioid Antagonism. A single oral dose of naltrexone hydrochloride 50 mg tablet will be administered by licensed study staff 2 hr (± 1 hr) before scan #2. Complete opioid receptor blockade is evident at 1-hour post-dose, which overlaps with time at maximum concentration in plasma (T_{max}) and persists for at least 24 hours post-dose in adults(13, 14). In our PK study in adolescents with ED, preliminary analysis shows T_{max} at 2 hour. Thus, optimal timing of 2 hours was conservatively chosen while providing a feasibility window supported by evidence. Naltrexone is well-tolerated and difficult to distinguish from placebo in blinded trials(15-17). CM IDS pharmacy will dispense study medication. Naltrexone hydrochloride 50 mg tablet is FDA approved for opioid and alcohol use disorder and used off-label for the treatment of compulsive and impulsive behaviors in children, adolescents and adults. Examples of compulsive and impulsive pertinent to this study include binge eating and purging (e.g., vomiting). Evidence for safe and efficacious use of naltrexone for these behaviors is available (4). This study does not significantly increase the risk associated with naltrexone as the commercially available dose, formulation and route chosen is consistent with current clinical practice at doses ranging from 50 -200 mg/day. Additionally, a meta-analysis revealed that naltrexone,

SHORT TITLE: Naltrexone Neuroimaging

when compared with placebo, is not associated with serious adverse events(17). It is not the intent of this study to generate data for submission to the FDA or to support a significant change in advertising of the drug. Storage, control and dispensation of the drug will occur through collaboration with IDS pharmacy. Use of naltrexone for this study meets criteria for IND exemption, category #1 (21 CFR 312.2(b)(1)).

Meals. Imaging will occur in the fed state using a standardized meal to avoid prolonged fasting that may compromise the health and recovery of the target population. This is not expected to meaningfully interfere with the detection of reward system modulation within individuals. Previous fMRI studies in adults suggest that individuals with disordered eating and/or obesity/overweight may exhibit stronger reward activation in the fed state compared with healthy controls(18, 19). Healthy weight individuals still exhibit strong reward activation, particularly in the ACC, in the fed versus fasted state, even though small reductions are seen(20).

Systemic Drug Exposure-Response Linkage. Plasma and urine will be obtained to measure systemic exposure to naltrexone and its primary, active metabolite, 6-beta-naltrexol, using a validated UPLC-MS/MS assay. Blood samples (3 mL) will be obtained from a peripheral intravenous catheter (PIV) to minimize discomfort associated with repeated blood draws (**Table 1**). *Genomic Variation.* To understand the impact of genetic variation on the naltrexone exposure-response relationship, DNA will be extracted from whole blood and genotyped for variants of interest.

Exploratory Assessments.

Total blood sampling. No more than 8 teaspoons (40 ml) of blood will be obtained during the study visit (9 PK time points, 1 genomic sample, 2 metabolomic samples, each 3 ml).

Compensation. Participants will be given \$400 via greenphire or CM preferred mechanism for completion of Study Day 1.

Biosafety Information. This study will involve handling, processing and transporting human biosamples from Hoglund to CMRI Clinical Pharmacology labs. Biosafety regulations will be followed.

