10.0 Risks to Subjects and Mitigation Strategies

- Small risk of loss of confidentiality, but every effort will be made to prevent this and keep participant information confidential. If the participant/LAR wish provides an email address and/or phone number, the study team may communicate with them and they will be informed that this is not a secure method and could be accessed by someone else in the event of a security breach. The hospital is not liable for security breaches.
- Minimal discomfort or bruising may occur with drawing blood and IV placement. The participant may be given the option of a numbing agent to help ease the pain of needle sticks.
- When answering the brief questionnaires, the questions asked may be uncomfortable or embarrassing. These risks are minimum and unlikely to occur. The participant does not have to give any information they do not want to give. Confidentiality will be protected to the greatest extent possible and answers will not be released to the care team.

SHORT TITLE: Naltrexone Neuroimaging

- Side effects to naltrexone occur in ~10% of patients, are typically mild and go away on their own (e.g., nausea) and do not differ from those receiving a placebo (e.g., sugar pill). Allergic reaction to naltrexone is rare and usually happens right away after taking the medicine. Symptoms include hives and difficulty breathing. Medications for immediate treatment of severe allergic reactions and trained personnel will be available in the clinic where the study drug is given.
- Genetic testing carries the possibility of discrimination. However, a Federal law called the Genetic Information Nondiscrimination Act (GINA) generally makes it illegal for health insurance companies, group health plans, and most employers to discriminate based on genetic information. Additionally, results will be kept in the study record and not released to your medical record.
- Incidental finding from the neuroimaging (e.g., fMRI) may occur. Whenever brain imaging is done, there is a chance of finding something unexpected and unrelated to the research study that may have some clinical implications. The neuroimaging used in this study is for research purposes only and is not the same as clinical neuroimaging.

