11.0 Potential Benefits

Participants have the possibility of direct benefit should they experience eating disorder symptom reduction after taking naltrexone (e.g. reduced urge to binge and/or purge or lack of positive reinforcement from binge/purge). It is plausible to experience an effect after a one-time dose based on evidence of complete opioid antagonism as soon as 2 hours after a one-time dose(13, 14). Should individuals experience a benefit, they may choose to share this information with their treating clinician and consider initiating ongoing therapy with naltrexone. Sharing such information with the treating clinician is outside the scope of this study and would solely be at the discretion of the participant.

The knowledge gained from this study has the potential to further our understanding of alterations in the reward pathway and their contribution to eating disorder and benefit society through advancement of mental health knowledge and treatment.

12.0 Investigator Assessment of Risk/Benefits Ratio:

Select as applicable:	Pediatric Risk Category:	
	Category 1	Research not involving greater than minimal risk (45 CFR §46.404 and 21 CFR §50.51)
	Category 2	Research involving greater than minimal risk but presenting the prospect of direct benefit to the individual subjects. (45 CFR §46.405 and 21 CFR §50.52)
	Category 3	Research involving greater than minimal risk and no prospect of direct benefit to individual subjects, but likely to yield generalizable knowledge about the subject's disorder or condition. (45 CFR §46.406 and 21 CFR §50.53)
	Category 4	Research not otherwise approvable which presents an opportunity to understand, prevent, or alleviate a serious problem affecting the health or welfare of children. (45 CFR §46.407 and 21 CFR §50.54)
Select if applicable:	Adult Risk Category:	
	Not Greater than Minimal Risk	
	Greater than Minimal Risk	

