23.0 Adverse Events and Unanticipated Problems

Any adverse event that occurs during study participation will be recorded. The primary safety end point will be based on frequency of AEs during the Study Day.

Definition and Grading Intensity of Adverse Events

An adverse event is defined as any undesired change in the body structure (signs) or body function (symptoms), whether or not considered drug-related. For the purposes of this study, drug-related is independent from study-related, as described above. During the entire duration of the study, subjects will be instructed to report all adverse events. All adverse events, whether volunteered, elicited, or noted on physical examination, will be recorded throughout the study. Each adverse event will be described by 1) its duration 2) severity grade (see below for definition), 3) its relationship to the medication studied (none, possible, probable, definite) 4) the action(s) taken.

The severity of adverse events will be categorized as follows:

SHORT TITLE: Naltrexone Neuroimaging

- MILD = Experience is minor and does not cause significant discomfort to subject or change in activities of daily living (ADL); subject is aware of symptoms but symptoms are easily tolerated.
- MODERATE = Experience is an inconvenience or concern to the subject and causes interference with ADL but the subject is able to continue with ADL.
- SEVERE = Experience significantly interferes with ADL and the subject is incapacitated and/or unable to continue with ADL.

Serious Adverse Event (SAE) Reporting

A serious adverse drug experience (by FDA definition) is any adverse test material event occurring at any dose that results in any of the following outcomes:

- Death
- Life-threatening adverse experience
- Inpatient hospitalization or prolongation of existing hospitalization
- Persistent or significant disability/incapacity
- Congenital anomaly/birth defect

Any serious adverse event will be reported verbally to the primary investigator (see contact info below) and naltrexone prescriber within 24 hours of notification. Written notification will be sent to the IRB within 3 working days.

[name], APRN [REDACTED], [contact]

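### The only post-dose safety check whose content is named covers physical symptoms, so worse mood, distress or binge/purge urge may be less completely solicited in the Study Day adverse event frequency

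*Combined protocol and SAP*

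**What the plan says.** Section 9 (Assessments, Safety) lists two items. One is baseline heart rate and blood pressure. The other is: "Physical symptoms that may occur after naltrexone administration will be assessed". It gives no checklist, method or time points.

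Section 23 sets the end point and the rules for capture:

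- "The primary safety end point will be based on frequency of AEs during the Study Day".
- An adverse event is "any undesired change in the body structure (signs) or body function (symptoms), whether or not considered drug-related". Mental state and behaviour are neither named nor excluded.
- On reporting by participants: "During the entire duration of the study, subjects will be instructed to report all adverse events". No type of event is excepted.
- On the routes by which events are captured: "All adverse events, whether volunteered, elicited, or noted on physical examination, will be recorded throughout the study". What is elicited, and when, is not stated.

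Elsewhere in Section 9, the EPSI is a baseline measure, and the impulsiveness, negative urgency and delayed discounting measures sit in the pre-dose row of the visit table. The only self-report that the table shows after dosing is the hunger rating at scan #2, which is not listed under Safety.

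Section 11 describes the prospect of "direct benefit should they experience eating disorder symptom reduction after taking naltrexone (e.g. reduced urge to binge and/or purge", and adds: "It is plausible to experience an effect after a one-time dose".

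**The concern.** How often an event is found depends on whether people are asked. A symptom within the stated scope of an assessment is likely to be raised with each participant. One outside that scope depends on the participant deciding that it is worth mentioning. The stated scope here is physical, while the sample is people aged 13 to 21 with binge/purge disorders who eat two study meals and view food pictures in two scans on one day.

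The plan is also one-sided on urge. A fall after dosing is offered as the possible direct benefit, yet no visible text schedules a question that would pick up a rise. If the study ends with no reported psychological worsening, that result is reassuring only if everyone was asked. The Study Day is the scheduled opportunity, because under Section 24 the monitoring committee learns of later events only when a participant makes contact.

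**Working it through.** The plan states no figure to reproduce on this point. The check is a comparison of the routes by which an event can reach the safety end point.

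| Route | Physical symptoms | Mood, distress, urge |
|---|---|---|
| Named post-dose assessment (Section 9, Safety) | Yes | Not named |
| Volunteered (Section 23) | Yes | Yes, if the participant sees it as an adverse event |
| Elicited (Section 23) | Yes | Possible; content and timing not stated |
| Noted on physical examination (Section 23) | Yes | Less likely to show |
| Post-dose self-report in the visit table (Section 9) | Hunger only | None |

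**Step 1: is psychological worsening excluded?** No. Section 23 records all adverse events however they arise. Its definition can be read to include a stronger urge, since Section 11 treats a weaker urge as a reduction in symptoms. It does not say so outright.

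**Step 2: is it solicited to the same extent?** Not on the visible text. Physical symptoms have a named assessment; mood, distress and urge have only the general routes.

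**Step 3: can the difference be sized?** No. That needs the rate of these events and the share that surfaces without a question, and the documents give neither. For scale only:

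- With the maximum of 50 participants (Section 5), one missed participant is 1/50 = 2 percentage points of the proportion with any adverse event. This holds only if that participant has no other recorded event. If frequency means a count of events, the step is one event.
- Section 10 puts naltrexone side effects at about 10% of patients, which is 0.10 × 50 = 5 participants.

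**Step 4: where do questions fit in the day?** The inputs are the visit table and the dosing window in Section 9.

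- Baseline measures are at 8:20 am and scan #1 is at 9:00 am.
- The dose is at 10:30 am. Scan #2 starts at 12:30 pm and lasts about 1 hour, so it ends at about 1:30 pm. That is 10:30 am + 3 h, the 3-hour draw.
- The last draw is at 10:30 am + 7 h = 5:30 pm.
- Dosing may be 2 h ± 1 h before scan #2, so the scan can start 1 to 3 h after the dose and end about 2 to 4 h after it. The middle question should therefore be tied to the end of scan #2. If the scan runs late, the 4-hour draw (2:30 pm) serves.

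**The case against.** The strongest reply is that Section 23 governs the end point and already covers this: every adverse event is to be reported and recorded whether or not it is drug-related, and Section 24 sends all of them to the committee. That stands against any claim of exclusion. A reader might infer that psychological or behavioural events are not collected, and the documents contradict that. It does not meet the narrower point, because general reporting is not the same as asking everyone.

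A second reply is that Section 9 names a category and not a list, so one general question might cover both kinds of symptom in practice. That is possible, and it is why the conclusion says *may*.

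A third is that text is missing. The heading Exploratory Assessments has nothing visible under it. References 21 to 28, on impulsiveness, negative urgency, negative affect and delay discounting, are cited nowhere in the visible text. The visit table is not exhaustive either: it omits the EPSI, the vital signs and the physical-symptom check itself. So an unseen post-dose item cannot be ruled out. The visible table does place the impulsiveness, urgency and discounting measures before dosing.

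A fourth is proportion. This is one 50 mg dose in a pilot, Section 4 lists no safety outcome, and Section 10 says side effects do not differ from placebo. This limits the weight of the point. A reader might also infer that a single dose is expected to worsen mood or urge; nothing in the documents says so.

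A fifth concerns the remedy. Questions about urge between the two scans would precede scan #2 but not scan #1, adding an asymmetry to an uncontrolled pre/post %BOLD comparison. This is right, and it determines where the questions should go.

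**Conclusion.** The point holds as uneven solicitation. Physical symptoms have a named post-dose assessment. Worse mood, distress or urge can be recorded, but no visible text has each participant asked about them, although the plan itself regards urge as something that one dose may change. The Study Day adverse event frequency may therefore capture these events less completely.

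The amount cannot be calculated, and a reader should not infer a known bias in the end point. The impact is modest. The conclusion rests on two assumptions: that staff will follow the stated scope of the Section 9 assessment, and that the text not visible under Exploratory Assessments holds no post-dose question on mood or urge. The change is worth making because it costs little and makes a finding of no worsening interpretable.

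**What to change.** 1. In Section 9 (Safety), widen the assessment to physical and psychological symptoms, including mood, distress and urge to binge or purge. Existing staff ask at three existing contacts: with the other pre-dose measures at about 8:20 am, before scan #1; after scan #2, at about the 3-hour draw (1:30 pm); and before discharge at the 7-hour draw (5:30 pm). Ask nothing about urge between the two scans, so that the pre/post %BOLD comparison is not affected. Anything that a participant volunteers in that interval is still recorded.
2. In Section 23, state that worsening from baseline in mental state or behaviour counts as an adverse event, and name who on site responds to a positive answer.

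The cost is a wording amendment and a few questions, with no new visit. A positive answer needs a staff response, and Section 23 already requires the action taken to be recorded for each event. There are three drawbacks. The reported adverse event frequency may rise. The baseline question follows a meal but no scan, so it does not match the question after scan #2. And without a control arm, worsening cannot be attributed to naltrexone as against the second meal, the second scan or the long day.
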